3.8. Analysis Windows

3.8.1. Definition of Study Day

Study Day 1/First Dose Date is defined as the day when the first dose of B/F/TAF was taken. The first dose date is the earliest nonmissing start date of B/F/TAF study drug recorded on the Study Drug Administration eCRF.

Study Days are calculated relative to Study Day 1. For events that occur on or after the Study Day 1 date, study days are calculated as (visit date minus Study Day 1 date plus 1). For events that occurred prior to Study Day 1, study days are calculated as (visit date minus Study Day 1 date).

Last Dose Date is defined as the maximum, nonmissing end date of B/F/TAF recorded on the Study Drug Administration eCRF and “Study Drug Permanently Discontinued” box checked for participants who prematurely discontinued study drug or completed study drug according to the Study Drug Completion eCRF.

For partial or missing last dose dates, please refer to the programming specifications for imputation rule details.

Last Study Date is the latest of the study drug start dates and end dates, the clinic visit dates, and the laboratory visit dates, including the 30-day follow-up visit date, for participants who prematurely discontinued study according to the Study Completion eCRF.

Baseline value is defined as the last value obtained on or prior to Study Day 1 for all assessments.

Note: for first dose date for SBR treatment group for listings, refer to the Week 48 SAP.

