7.2.1. Summaries of Numeric Laboratory Results

Descriptive statistics will be provided by treatment group (B/F/TAF, Delayed Switch to B/F/TAF) for each laboratory test specified in the study protocol as follows:

- Baseline values
- Values at each postbaseline analysis window
- Change from baseline at each postbaseline analysis window

A baseline laboratory value will be defined as the last nonmissing value obtained on or prior to the date of first dose of study drug. Change from baseline to a postbaseline visit will be defined as the postbaseline value minus the baseline value. The mean, median, Q1, Q3, minimum, and maximum values will be displayed to the reported number of digits; SD values will be displayed to the reported number of digits plus 1.

In the case of multiple values in an analysis window, data will be selected for analysis as described in Section 3.8.3.

Calcium Corrected for Albumin

Calcium corrected for albumin will be calculated and summarized for the study. The following formula will be used when both serum calcium and albumin results for a given blood drawn are available and serum albumin value is < 4.0 g/dL.

- Calcium corrected for albumin (mg/dL) = serum calcium (mg/dL) + 0.8 × (4.0 - albumin (g/dL)).

Toxicity grading for calcium will be applied based on the corrected values.

Estimated GFR

The Cockcroft-Gault (CG) formula will be used to calculate eGFR_{CG}:

- eGFR_{CG} (mL/min) = [(140 - age (yrs)) × weight (kg) × (0.85 if female)] / (SCr (mg/dL) × 72), where weight is total body mass in kilograms, and SCr is serum creatinine.

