7.2.2.1. Treatment-Emergent Laboratory Abnormalities

Treatment-emergent laboratory abnormalities are defined as values that increase at least 1 toxicity grade from baseline at any postbaseline time point, up to the cutoffs specified at the start of Section 7.2.

If the relevant baseline laboratory value is missing, any abnormality of at least Grade 1 observed within the time frame specified above will be considered treatment emergent.

Fasting glucose and nonfasting glucose (including glucose results without a known fasting status) are graded based on different grading scales as specified in the protocol. Most participants had a nonfasting glucose at the Screening visit and a fasting glucose at the Day 1 visit; therefore, both a baseline nonfasting glucose and a baseline fasting glucose are available for most participants, and treatment-emergent laboratory abnormalities will be summarized for both nonfasting glucose and fasting glucose.

Both urine RBC based on microscopic examination, labeled as Hematuria (Quantitative), and urine blood based on a dipstick, labeled as Hematuria (Dipstick), are assessed and assigned a toxicity grade in this study. Hematuria (Quantitative) is a reflex test. Urine RBC based on microscopic examination or Dipstick will be presented in laboratory toxicity summary tables and listings.

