Note: Prothrombin Intl. Normalized Ratio (INR) and Prothrombin Time (PT) were graded based on the protocol defined toxicity grade scale. The results and toxicity grade will be listed in listing, but not be summarized in lab toxicity summary table.

Due to the reflexive nature of the quantitative urine RBC test, results will be combined with the dipstick test of urine blood as described below. General rule is that urine RBC (Quantitative) should always be used first (if available), no matter if it is collected at the same time of Urine Blood (Dipstick) or not. The combined Urine RBC (hematuria, Quantitative or Dipstick) toxicity grade will be used for “Maximum treatment-emergent toxicity grade” summary.

Is Post-BL Urine RBC (Quant.) Result Available?	Is BL Urine RBC (Quant.) Result Available?	Is Post-BL Urine Blood (Dipstick) Result Available?	Is BL Urine Blood (Dipstick) Result Available?	How to Determine Treatment-Emergent Toxicity for “Urine RBC (Hematuria, Quantitative or Dipstick)”
Yes	Yes			Compare post BL Urine RBC (Quant.) toxicity grade to BL Urine RBC (Quant.) toxicity grade. If post BL toxicity is greater than BL toxicity, then treatment emergent
Yes	No			Treatment emergent. Use post BL Urine RBC (Quant.) toxicity grade.
No		Yes	Yes	Compare post BL Urine Blood (Dipstick) toxicity grade to BL Urine Blood (Dipstick) toxicity grade. If post BL toxicity is greater than BL toxicity, then treatment emergent
No		Yes	No	Treatment emergent. Use post BL Urine Blood (Dipstick) toxicity grade.
No		No		Do not count participant in the denominator for “Urine RBC (Hematuria, Quantitative or Dipstick)”

BL Baseline. Quant Quantitative. “ ” means any value can be present (or it can be missing), as it does not affect the classification

14) Concomitant nonstudy drug ARV medications (ie, ARV medications other than study drug that are taken while receiving study drug) will be flagged in “Nonstudy Drug Antiviral Medication” listing. The logic to define concomitant nonstudy drug ARV is similar to concomitant non-ARV Medications (see details in Section 7.4.2)

15) Lipid modifying medication analyses:

- Lipid modifying medication is defined to be the concomitant medication with WHO Drug ATC2 term (drug class) “LIPID MODIFYING AGENTS” and WHO Drug preferred drug name (CMDECOD) contains wording of “STATIN” in the ADCM dataset.

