HBV DNA	GET1883	HBV DNA CAP/CTM 2.0 EDTA CL	“No HBV DNA detected”, “<20 IU/mL HBV DNA detected”, “>170000000”*, NUMERICAL VALUE (IU/mL)*
HBV DNA	GET1884	HBV DNA CAP/CTM 2.0DiI EDTA CL	NUMERICAL VALUE (IU/mL)*
HCVAb	CNT350	Hepatitis C Virus Antibody	“Positive”*, “Indeterminate”, “Negative”
HCV RNA	GET1881	HCV RNA CAP/CTM 2.0EDTA CL	“No HCV RNA detected”, “<15 IU/mL HCV RNA detected”, NUMERICAL VALUE (IU/mL)*

Note: HBVDNA AMPLIPREPTAQMANTM 2.0 DIL(GET1884) is for HBV DNA CAP/CTM 2.0 >170,000,000 IU/mL. HBsAg(ATT1) test is conducted when HBsAg(ATT2) results “Repeat reactive, confirmed”, “Repeat Reactive Unconfirmed”.

- For baseline coinfection, when considering the different laboratory tests, take the latest, non-missing record on or prior to the first dose date for each test (eg, HBsAg, HBsAb, HBcAb, and HBV DNA)

The baseline coinfection status will be one of the three values: Yes/No/Null

The following tables provide combinations of HBV and HCV tests and the corresponding baseline coinfection status

HBsAg	HBsAb	HBcAb	HBV DNA	Coinfection Status	
Positive				Y	
Negative	Positive			N	
	Negative	Positive	Quantifiable	Y	
			Not Quantifiable	N	
			Missing	Null	
		Negative		N	
		Missing	Missing	Quantifiable	Null
				Not Quantifiable	N
	Missing			Null	
	Missing	Positive	Quantifiable	Null	
			Not Quantifiable	N	
			Missing	Null	
		Negative		N	
		Missing	Missing	Quantifiable	Null
				Not Quantifiable	N
	Missing			Null	
Missing	Positive			Null	
	Negative	Positive	Quantifiable	Y	
			Not Quantifiable	Null	
			Missing	Null	
	Negative		Null		
	Missing		Null		
	Missing		Null		

HCVAb	HCV RNA	Coinfection Status
Positive	Quantifiable	Y
	Not Quantifiable	N
	Missing	Null
Negative		N
Missing	Quantifiable	Null
	Not Quantifiable	N
	Missing	Null

“ ” means any value can be present, as it does not affect the classification

- For incident coinfection, all laboratory tests must share the same accession number and if any set of values meets the criteria, then the participant is considered to have incident coinfection

The incident coinfection status will be one of two values: Yes/Null

The following tables provide combinations of HBV and HCV tests that are considered “Y” for incident coinfection status (all others are considered Null)

HBsAg	HBsAb	HBcAb	HBV DNA	Coinfection Status
Positive				Y
Negative	Negative	Positive	Quantifiable	Y
Missing	Negative	Positive	Quantifiable	Y

HCVAb	HCV RNA	Coinfection Status
Positive*		Y
	Quantifiable	Y

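### SAP Appendix 6 item 13 can carry an older quantitative urine RBC grade forward as the hematuria baseline after a newer negative pre-dose dipstick (minor)

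*SAP*

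**What the plan says.** Section 3.8.1 of the SAP sets the general rule: "Baseline value is defined as the last value obtained on or prior to Study Day 1 for all assessments". Section 7.2.1 repeats it for laboratory tests: "A baseline laboratory value will be defined as the last nonmissing value obtained on or prior to the date of first dose of study drug". Section 7.2.2.1 defines a treatment-emergent abnormality as a rise of at least one toxicity grade from baseline, and notes that "Hematuria (Quantitative) is a reflex test".

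Appendix 6 item 13 merges the quantitative and dipstick results into one table line. Its general rule is that "urine RBC (Quantitative) should always be used first (if available), no matter if it is collected at the same time" as the dipstick or not. Two rows of its decision table matter here:

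- Row 1, quantitative result present both before and after baseline: "Compare post BL Urine RBC (Quant.) toxicity grade to BL Urine RBC (Quant.) toxicity grade". The dipstick columns are blank, which the footnote defines as having no effect on the classification.
- Row 2, quantitative result present after baseline only: "Treatment emergent. Use post BL Urine RBC (Quant.) toxicity grade". The dipstick columns are again blank.

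The baseline row of Table 3-1 has an upper limit of Day 1 and no lower limit, so an old result does not expire.

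**The concern.** A reflex test that was not triggered is informative: the urinalysis gave no reason to run it. Item 13 treats that situation as if no newer information existed and falls back on whatever quantitative result was last recorded. A participant with Grade 2 quantitative hematuria at Screening and a negative dipstick on Day 1 enters the table with a Grade 2 baseline, and a Grade 1 or 2 quantitative result on B/F/TAF is then not treatment-emergent.

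Study Day 1 in the final analysis is the first B/F/TAF dose, which falls at about Week 24 for Delayed Switch. That group has a longer pre-dose record, so it has more opportunity to pick up an out-of-date baseline. At stake is the accuracy of one safety line, shown for B/F/TAF, Delayed Switch and the pooled column.

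**Working it through.** The plan gives no figure to reproduce here. The check traces the rule through cases, counts opportunities, and then gives an illustrative size.

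**1. Tracing the rule.** Each participant below has a post-baseline quantitative result of Grade 1.

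| Older quantitative grade | Last pre-dose urinalysis | Item 13 | Baseline from last urinalysis |
|---|---|---|---|
| 2 | dipstick negative, no reflex | row 1: 1 is not above 2, not counted | baseline 0, counted |
| 0 | dipstick negative, no reflex | row 1: 1 is above 0, counted | baseline 0, counted |
| none | dipstick Grade 1, no quantitative result | row 2: counted | baseline 1, not counted |

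The first case is an undercount, the second is unaffected, and the third is an overcount. A case is lost only if the old quantitative grade is at least 1, the last pre-dose dipstick is negative without reflex, and no post-baseline quantitative grade exceeds the old one.

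**2. Opportunities.** Urinalysis is done at every visit (Protocol 6.9.2 and Appendix 2).

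- Immediate switch: Screening and Day 1, so 2 pre-dose urinalyses and 1 earlier than the last. Screening is at most 30 days before Day 1.
- Delayed Switch: Screening, Day 1, Weeks 4, 12 and 24, so 5 pre-dose urinalyses and 4 earlier than the last. The oldest can be about 30 + 168 = 198 days before the first dose.

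**3. Chance that the situation arises.** Let q be the probability that a visit yields a reflexed quantitative result, independent across visits, and m the number of pre-dose urinalyses. The chance of a negative last dipstick together with an older quantitative result is (1 − q) × [1 − (1 − q)^(m−1)].

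| q (assumed) | Immediate, m = 2 | Delayed Switch, m = 5 |
|---|---|---|
| 5% | 0.95 × 0.05 = 4.8% | 0.95 × (1 − 0.95⁴) = 17.6% |
| 10% | 0.90 × 0.10 = 9.0% | 0.90 × (1 − 0.90⁴) = 31.0% |
| 20% | 0.80 × 0.20 = 16.0% | 0.80 × (1 − 0.80⁴) = 47.2% |

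These are upper limits on the participants affected, because the other conditions in step 1 must also hold.

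**4. Illustrative effect on the table line.** I compared item 13 with a baseline from the last pre-dose urinalysis by simulation. Assumptions, none of them in the documents: dipstick positivity of 5 to 20% per visit; quantitative grades 0/1/2/3 at 30/40/25/5%; positive-dipstick grades 1/2/3 at 60/30/10%; visits independent or correlated within person; 7 post-baseline visits for immediate switch and 5 for Delayed Switch. Relative change in treatment-emergent hematuria under item 13:

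| Positive dipsticks without a quantitative result | Immediate | Delayed Switch |
|---|---|---|
| none | −2% to −9% | −9% to −25% |
| 30% | −0.4% to −2% | −4% to −12% |

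The grade mix matters as much as the reflex rate. At 10% positivity, within-person correlation 0.1 and full reflex, the loss is about 8% (immediate) and 28% (Delayed Switch) if every quantitative result is Grade 1 to 3. It is about 3.5% and 11% if 60% of them are Grade 0.

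**5. Which grades.** Hematuria has no Grade 4 in Protocol Appendix 4. A post-baseline Grade 3 is lost only if the old baseline was itself Grade 3, so the loss falls almost wholly on Grades 1 and 2.

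**The case against.** The strongest reply is that the SAP applies its last-value rule test by test. Section 7.2.2.1 keeps two glucose baselines from different visits because "both a baseline nonfasting glucose and a baseline fasting glucose are available for most participants", and the coinfection rules in Appendix 6 "take the latest, non-missing record on or prior to the first dose date for each test". On that reading the last quantitative result is simply that test's own last nonmissing baseline, and item 13 is a deliberate rule that compares like with like. This stands to the extent that a reader who infers an outright contradiction goes too far. It does not remove the problem. Fasting and nonfasting glucose are separate table lines, whereas hematuria is one combined line whose latest pre-dose assessment can be a dipstick that item 13 ignores. Elsewhere in Appendix 6, reflex HBV DNA results are linked to the original sample by accession number, as are the tests for incident coinfection.

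A second reply is that the net error is not fixed. Row 2 overcounts when a positive baseline dipstick has no quantitative result, and neither the reflex trigger nor the frequency of hematuria is given. This stands. A reader might infer that the SAP undercounts hematuria as a general matter; the documents support only a conditional undercount.

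A third reading is that the rule makes Delayed Switch look misleadingly better. Most of any such gap comes from unequal follow-up. At 10% positivity, independent visits and full reflex, the last-urinalysis rule gives 38.0% and 29.0%, a gap of 9.0 points with no drug effect assumed. Item 13 gives 36.2% and 24.3%, a gap of 11.9 points. About three quarters (9.0/11.9) remains after the fix, and the SAP plans no formal comparison of these columns.

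Finally, a baseline drawn from either test can set a dipstick grade against an RBC/HPF grade. That is a real cost, though limited: for a negative dipstick the fix gives the classification that row 2 already gives.

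**Conclusion.** Item 13 as written allows an older graded quantitative result to stand as the hematuria baseline over a newer negative pre-dose dipstick. This departs from the last-value intent of Sections 3.8.1 and 7.2.1 without saying so. The mechanism and the greater opportunity in Delayed Switch (4 earlier urinalyses against 1) follow from the SAP text and the visit schedule alone.

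The size does not. In every scenario tried the net effect was an undercount, larger in Delayed Switch, but all the percentages rest on assumed positivity, grade mix and reflex rate. Because row 2 can act in the opposite direction, the documents do not strictly fix even the sign. The consequence is confined to one line of a descriptive table. No endpoint, test or decision depends on it, and the by-subject urinalysis listings still show every result. Severity: minor.

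**What to change.** In Appendix 6 item 13, define the baseline for the combined hematuria line as the latest urinalysis on or before the first B/F/TAF dose, and grade it as follows:

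- If a quantitative test was reflexed from that sample, use its quantitative grade.
- If the dipstick was negative and no reflex was triggered, use Grade 0, and do not carry forward an older quantitative result.
- If the dipstick was positive but has no quantitative result, use the dipstick grade and footnote the cross-scale comparison.

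For baseline, delete the clause that gives the quantitative result priority irrespective of when it was collected. The second bullet removes the out-of-date baseline and the third removes the row 2 overcount.

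The cost is a small programming change on data already collected, plus occasional comparisons of a dipstick grade with a quantitative grade.

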— HBV blood panel (**Screening and Week 48**): Hepatitis B virus surface antigen (HBsAg), Hepatitis B virus surface antibody (HBsAb) and Hepatitis B virus core antibody (HbcAb)

The following tests will be conducted by the central laboratory if the following criteria are met:

- *If positive HBsAg*: reflex testing for plasma HBV DNA, Hepatitis B virus e-antigen (HBeAg) (if negative, reflex Hepatitis B virus e-Antibody [HBeAb]), and quantitative HBsAg

- *If positive HBcAb with negative HBsAg and negative HBsAb*: reflex testing for plasma HBV DNA (if positive, reflex HBeAg). If HBeAg is performed and found to be negative, reflex HBeAb
- Plasma HBV DNA for patients who are HBV co-infected (**Day 1, Week 24, Week 48, and ESDD**)

HBV coinfection, for the purposes of this study, is defined as any one of the following two criteria on or prior to Day 1:
 1. Positive HBsAg
 2. Negative HBsAg, negative HBsAb, positive HBcAb and quantifiable HBV DNA (HBV DNA ≥ 20 IU/mL)
- HCV antibody (Ab) serology (**Screening, Week 48, and Week 72**). Participants who are HCVAb positive will have a HCV RNA test performed.
- Mandatory Whole blood for HIV-1 DNA archive testing (**Day 1 for all participants, and at Week 24 for participants randomized to SBR only**)
- **CCI** [REDACTED]
- Plasma and serum storage sample for safety, virology, or PK testing (Not collected at Screening and 30-day Follow-up Visits)

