For other numeric observations (ie, except HIV-1 RNA, CD4+ cell count, CD4%, and HBV DNA), the record(s) collected on the day closest to the nominal day for that visit will be selected. If there are 2 days equidistant from the nominal day, the later day will be selected.

For any numeric observations except HIV-RNA, if there are multiple records on the selected day, the average will be taken.

- For baseline and postbaseline HIV-1 RNA, the latest (considering both date and time) record(s) in the window will be selected. If both “HIV RNA Taqman 2.0” and “HIV RNA Repeat” (ie, the HIV-1 RNA result obtained from an additional aliquot of the original sample) are available with the same collection time, the results from the “HIV RNA Repeat” will be selected for analysis purposes; otherwise, if there are multiple “HIV RNA Taqman 2.0” records with the same collection time, the geometric mean will be taken for analysis purposes.

If multiple valid nonmissing categorical observations exist in a window, records will be chosen as follows:

- For baseline, the last available record on or prior to the first dose date of study drug will be selected. If there are multiple records with the same time or no time recorded on the same day, the value with the lowest severity will be selected.
- For postbaseline visits, the most conservative value within the window will be selected.

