8. SPECIAL POPULATION ANALYSES

8.1. Analyses for HIV/HBV Coinfected Participants

Participants with HIV/HBV coinfection at baseline are defined as participants who meet any of the following two criteria:

- Positive HBsAg on or prior to the first dose date, or
- Negative HBsAg, negative HBsAb, positive HBcAb, and quantifiable HBV DNA (ie, HBV DNA \geq 20 IU/mL) on or prior to the first dose date.

The following analyses will be conducted by treatment (B/F/TAF, and Delayed Switch to B/F/TAF) for participants with HIV/HBV coinfection at baseline:

- Treatment-emergent adverse events overall summary
- Treatment-emergent adverse events by SOC, HLT, and PT
- Treatment-emergent laboratory abnormalities
- The change from baseline for liver-related laboratory tests, including ALT, AST, ALP, total bilirubin, direct and indirect bilirubin.

Listings will be provided for:

- adverse events
- liver-related laboratory tests and HBV DNA results
- ALT elevation (ie, ALT $>$ 2 x Baseline and ALT $>$ 10 x ULN) and ALT flare (see section [7.2.4](#))

Participants with incident HIV/HBV coinfection while on study drug are defined as participants who are not HIV/HBV coinfecting at baseline and meet any of the following criteria:

- Positive HBsAg after the first B/F/TAF dose date and on or prior to the last B/F/TAF dose date, or
- Negative HBsAg, negative HBsAb, positive HBcAb, and quantifiable HBV DNA (ie, HBV DNA \geq 20 IU/mL) after the first B/F/TAF dose date and on or prior to the last B/F/TAF dose date, or

- Experience any of the following adverse events (ie, selected MedDRA PTs from the SMQ of “Liver Infections”) with onset date after the first B/F/TAF dose date and on or prior to the last B/F/TAF dose date: Acute hepatitis B, Chronic hepatitis B, Congenital hepatitis B infection, Hepatitis B, Hepatitis B core antibody positive, Hepatitis B DNA assay positive, Hepatitis B surface antigen positive, Hepatitis B virus test positive.

The following listings will be provided for participants with incident HIV/HBV coinfection while on study drug:

- Listing of adverse events
- Listing of liver-related laboratory tests and HBV DNA results

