- Participants who took lipid modifying medications at baseline refer to the participants who have any use of the lipid modifying agents at Study Day 1.
 - a) More specifically, participants with “Lipid Modifying Agent Use at Baseline” include those participants in the B/F/TAF safety analysis set meeting both of the following criteria: 1) any selected CM record with the start date \leq the first dose date, and 2) the end date of the selected CM record \geq the first dose date or the end date of the selected CM record is ongoing

- b) For lipid modifying medications with the start date completely unknown, assume the start date is on or before the first dose date; lipid modifying medication is considered as being taken at baseline if the end date is not prior to the first dose date (ie, the end date is on or after the first dose date, completely unknown, or ongoing).
 - c) Lipid modifying medications with the start date prior to the first dose date and the end date unknown (completely missing) are considered as being taken at baseline (the unknown end date is assumed to be on or after the first dose date).
- Participants who initiated lipid modifying medications during the study are defined as the participants in the B/F/TAF safety analysis set who did not take lipid modifying medications at baseline and met the following criteria: any selected CM record with start date after the first B/F/TAF dose date and on and prior to the last B/F/TAF dose date.
- 16) For figures, if at a visit where n (sample size) for any treatment group < 5, data for that treatment group will not be displayed at that visit in the figure, but all data will be included in the corresponding table summary.
- 17) Vital signs and weight, height, BMI will be in the same listing.
- 18) HIV/HBV and HIV/HCV Coinfection:
- The following table presents the HBV and HCV tests with all possible values. Values that have an asterisk after them denote a “positive” (or “quantifiable” for HBV DNA and HCV RNA) result while all others denote a “negative” result.

Label	LBTESTCD	LBTEST	Possible Values
HBsAg	ATT1	Hep.B Surf.Ag Quant(70)CL	NUMERICAL VALUE or “<0.05” or “>124925.00” (IU/mL)
HBsAg	ATT2	Hep. B Surf. Ag Qual(70) CL	“Repeat reactive, confirmed”*, “Repeat Reactive Unconfirmed”, “Non Reactive”
HBsAb	CNT353	anti Hep B Surface Ag2 Qual	“Positive”*, “Negative”
HBcAb	CNT68	Hepatitis B Core Total	“Positive”*, “Negative”

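### SAP Appendix 6 item 18 codes every quantitative HBsAg result as negative, so a confirmed HBsAg-positive participant can be classed as not HBV-coinfected at baseline

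*SAP*

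**What the plan says.** SAP Appendix 6 item 18 tabulates the hepatitis B and C tests with their possible values. An asterisk marks a positive or quantifiable value, "while all others denote a “negative” result". Two rows carry the label HBsAg:

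- ATT1, quantitative: "NUMERICAL VALUE or “<0.05” or “>124925.00” (IU/mL". No value in this row has an asterisk.
- ATT2, qualitative: "Repeat reactive, confirmed”*, “Repeat Reactive Unconfirmed”, “Non Reactive". Only the first value has an asterisk.

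The table note says when the quantitative test is done: "HBsAg(ATT1) test is conducted when HBsAg(ATT2) results “Repeat reactive, confirmed”, “Repeat Reactive Unconfirmed". Protocol 6.9.1 likewise lists quantitative HBsAg among the reflex tests that follow a positive HBsAg ("HBeAb]), and quantitative HBsAg").

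For baseline coinfection, item 18 takes the latest non-missing record up to the first dose for each test. It names HBsAg as one such test, and the status table has a single HBsAg column. Where categorical baseline records share a time, or fall on the same day with no time, SAP 3.8.3 says that "the value with the lowest severity will be selected".

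SAP 8.1 defines baseline coinfection by either of two criteria. The first is "Positive HBsAg on or prior to the first dose date, or" and it carries no further condition. Protocol 6.9.1 has the same criterion.

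**The concern.** Under the asterisk rule, a quantitative HBsAg above the upper limit of the assay is a negative HBsAg. Because the assay is triggered by a reactive qualitative test, these nominal negatives arise only in participants whose qualitative result was reactive. The coinfection table then needs one HBsAg value from two records that disagree by construction, and the only general tie rule favours the less severe value.

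A participant wrongly set to N would drop out of the baseline coinfection count (SAP 5.2), the HBV adverse-event and laboratory summaries (SAP 8.1), and the ALT-elevation and ALT-flare listing, which is restricted to baseline coinfection (SAP 7.2.4). The same participant could also reappear as an incident HBV case on B/F/TAF.

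**Working it through.** The plan states no figure to reproduce. The check is to run the written rules on a participant whose ATT2 is confirmed reactive.

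**Step 1. Code the two records.** ATT2 confirmed reactive has an asterisk, so it is positive. Any ATT1 value has none, so it is negative. Lost asterisks in the PDF text are an unlikely explanation, because they survive in neighbouring rows. The HBV DNA row reads ">170000000”*, NUMERICAL VALUE (IU/mL" and closes with an asterisk, and numeric HCV RNA is also asterisked.

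**Step 2. Select one HBsAg value.** If ATT1 and ATT2 are pooled as HBsAg with tied times, and negative is taken as the lower severity, SAP 3.8.3 selects negative.

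**Step 3. Read the status table, complete data.** There are 2 × 2 × 2 = 8 patterns of HBsAb, HBcAb and HBV DNA.

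| HBsAb | HBcAb | HBV DNA | Status, HBsAg positive | Status, HBsAg negative |
|---|---|---|---|---|
| + | + | quantifiable | Y | N |
| + | + | not quantifiable | Y | N |
| + | − | quantifiable | Y | N |
| + | − | not quantifiable | Y | N |
| − | + | quantifiable | Y | Y |
| − | + | not quantifiable | Y | N |
| − | − | quantifiable | Y | N |
| − | − | not quantifiable | Y | N |

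The result moves from 8 Y to 7 N and 1 Y.

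**Step 4. Allow missing results.** With three levels each there are 3 × 3 × 3 = 27 patterns. With HBsAg positive, all 27 are Y. With HBsAg negative:

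- HBsAb positive: 9 N.
- HBsAb negative: 1 Y, 5 N, 3 Null.
- HBsAb missing: 5 N, 4 Null.

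The total is 9 + 5 + 5 = 19 N, 3 + 4 = 7 Null and 1 Y. All of these are counts of table cells, not expected shares of participants.

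**Step 5. Compare with the definition.** SAP 8.1 and Protocol 6.9.1 make the same participant coinfected in every pattern, because a positive HBsAg is sufficient. The row with HBsAb negative, HBcAb positive and HBV DNA not quantifiable shows the conflict most plainly: Y by definition, N by the table. It is a plausible profile, since participants with chronic HBV may enrol only on TAF or TDF, although no document says how common it is.

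**Step 6. Try the other reading.** If each test means each test code, both HBsAg records are kept and no tie arises. One positive and one negative then feed a single column, and item 18 gives no rule to combine them. The appendix does set precedence elsewhere: item 19 says which HBV DNA code governs, and the hematuria rule in item 13 uses the quantitative result first.

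**Step 7. Follow the error forward.** Incident HBV requires no coinfection at baseline and a later qualifying set of results, and any such set counts. The HBV panel is repeated at Week 48, so a confirmed ATT2 there would make a wrongly N participant incident. For HCV, a footnote blocks this by requiring a negative or missing baseline antibody. HBV has no such guard.

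**The case against.** The best reply is that the SAP never directs this misclassification. It takes three unstated steps: pooling two codes that have separate test names, applying a categorical tie rule when ATT1 is a numeric result (SAP 3.8.3 averages numeric baseline ties and has no rule for a mixed pair), and ranking negative as the lower severity, although no severity order is given for HBsAg. A programmer who works from SAP 8.1, or from ATT2 alone, classifies correctly. The missing ATT1 asterisk may even be deliberate: ATT1 also follows an unconfirmed reactive ATT2, and asterisks on its values could turn those participants positive.

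Much of this stands, and it is why the point says that the error can occur, not that it must. It does not remove the point. Item 18 itself declares ATT1 values negative under the label HBsAg, the status table has one HBsAg column, and a reflex result on the same sample would naturally share its collection time. If ATT2 was meant to decide alone, the text does not say so.

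A reader might go further and infer that every HBsAg-positive participant is lost, or that most are because they enter on TAF or TDF. The documents do not support either. The error is conditional, one complete-data pattern stays Y, and no HBV suppression rate or count of HBsAg-positive participants is given. Nor does quantifiable HBV DNA protect the classification in general: it does so only with HBsAb negative and HBcAb positive.

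**Conclusion.** Wrong as written. The literal mapping of ATT1 conflicts with the SAP's own definition of baseline HBV coinfection, and no rule says which HBsAg code governs.

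The misclassification itself rests on three assumptions: the codes are pooled, their times tie (or no time is recorded on the same day), and negative counts as the lower severity. Under these, with complete data, a confirmed HBsAg-positive participant becomes N unless HBsAb is negative, HBcAb is positive and HBV DNA is quantifiable. Some missing-data patterns give Null. Participants whose ATT2 is reactive but unconfirmed are not misclassified, because the table already treats them as negative.

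The reach is narrow: the baseline coinfection count, the HBV-subgroup adverse-event and laboratory summaries, the ALT-flare listing, and possible false incident HBV cases at a later panel. The number affected cannot be estimated from the documents. The efficacy endpoints do not depend on this status, the overall safety tables still contain these participants, and on-study handling of ALT flares follows the protocol, not this table.

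**What to change.** In Appendix 6 item 18, state that:

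- HBsAg status comes from ATT2 only, with the confirmed repeat-reactive value as positive and the other two as negative;
- ATT1 is listed but not used for status;
- the SAP 3.8.3 tie rule does not apply between ATT1 and ATT2.

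With this wording, a confirmed reactive ATT2 gives Y in 27 of 27 patterns, in line with SAP 8.1 and Protocol 6.9.1. As a check, cross-tabulate the selected baseline ATT2 result against the derived coinfection flag: every confirmed reactive participant should be Y.

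The cost is programming-specification wording, with no new data. SAP Section 1 already provides for documenting changes after finalization in the clinical study report.
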